Aim 3 analysis will follow analytic procedures to address the dimension of Effectiveness from our conceptual framework. For comprehension, concordance between patient responses and information from genetic counselors' notes will be scored. We will test bivariate relationships between the outcome variables and study arm using Student's t-test or the nonparametric Wilcoxon rank-sum test between continuous variables, and chi-square test (or Fisher's exact test if small cell counts) for categorical data. We will examine distributions for continuous outcomes and transform the data if skewed. Procedures for building multilevel multivariable linear (continuous outcomes) or logistic (binary outcomes) regression models are described above. Regression models extended to include random effects for clinic or provider will be fit using software for linear mixed models for continuous outcomes and generalized linear mixed models for categorical outcomes. As with Aim 2, we will examine effect modification by testing for significant interactions between variables in regression models.

Aim 3 Sample Size

We estimate a sample size of 1,100 for a multilevel multivariable regression analysis with >90% power to detect a small effect size (0.02) attributable to 2 independent variables using an F-Test with an alpha of 0.05 using PASS 15 Software. The variables tested are adjusted for an additional 20 independent variables. To examine effect modification sample size is calculated based on logistic regression of a binary response variable (Y) on a binary independent variable (X) and a binary confounder variable (Z) with a sample size of 1,710 observations achieves 80% power at a 0.05 significance level to detect the X-Z interaction odds ratio of 1.5. Calculations assume that a two-sided Wald test is used.

IRB_00123563

Created: 6/5/2019 3:01
PM

IRB_00123563

- Request for Waiver of Consent

PI: [name]

Submitted: 3/5/2019

Title: Broadening the Reach, Impact, and
Delivery of Genetic Services**Request for Waiver or Alteration of Consent***** Requested Waivers**

Date Created	Type of Request	Purpose of Waiver Request
View 3/18/2019	Waiver of Informed Consent	Waiver of consent for chart review without patient contact

IRB_00123563

Created: 6/5/2019 3:01 PM

PI: [name]

Submitted: 3/5/2019

IRB_00123563

IRB Smart Form

Title: Broadening the Reach, Impact, and Delivery of Genetic Services

Request for Waiver or Alteration of Consent

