We would like to collect the following information on patients identified to meet criteria in order to determine eligibility, invite them to participate, and to be able to compare those who participate and those who decline:

Name and contact information
Demographics
Race/ethnicity
Prior referral to genetic counseling
Family history
Genetic counseling and testing
Primary care provider
Date of last appointment
History of reading and responding to messages via the patient portal
Other health conditions

Identifiers will be deleted from the research record, but we will keep the other information used in planning patient recruitment in order to compare differences between those who did and did not participate in the research questionnaires.

4. Explain why the PHI to be used or disclosed is the minimum necessary to accomplish the research objectives:

The PHI data will be used only to better define which populations are utilizing genetic services, and if different delivery models impact a patient's health or their primary care decisions.

5. Explain why the research could not practicably be conducted without the waiver of authorization. For example, complete the following sentence: "If I had to obtain authorization, the research could not be conducted because..."

The research could not be conducted because there is no other non-intrusive or unbiased way to determine patient adherence to recommendations from the genetic services.

Study team requests authorization to access patient EHR who participate in genetic services. If not, no insights can be gained to determine the efficacy of genetic services in different patient populations, as well as the impact of genetic counseling, testing and education in collaboration with primary care.

6. Describe your plan to protect the identifiers from improper use and disclosure, and indicate where the PHI will be stored and who will have access:

Study team will work closely with HCI FCAC genetic counselors and genetic counseling assistants to minimize PHI used in the research record. Unique

participant identifiers will be used as name-holders.

Only authorized personnel listed on this IRB application, with updated trainings, will have access to study data and tracking methods.

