Utah began enrollment for their pilot study in April 2020 and enrollment for their full study in November 2020. To date, appox. 450 participants have been invited to participate in Questionnaire #1 and 100 participants have been invited to participate in Questionnaire #2 at this site. Although delayed due to COVID-19, recruitment remains ongoing and enrollment has picked up during 2022.

NYU began enrollment for their pilot study in Dec 2020 and enrollment for the full study in February 2021. To date, 480 participants have been invited to participate in Questionnaire #1. The technical

implementation was substantially delayed at this site due to COVID-19 but recruitment and enrollment have been successful during 2022 and remains ongoing.

- **What results (preliminary or final) have been obtained from the study? If the study is part of a multi-center trial, this should be stated and any available results provided. If there are no results that are appropriate to report to the IRB at this time, this should be stated and explained:**

We will be conducting analysis after accrual is complete.

Please attach any abstracts or publications:

Name Version Date Created Date Modified Date Approved

There are no items to display

- **Describe participant enrollment and its effect on the study design and scientific merit. If under accrued, describe any plans for increasing enrollment during the next approval period. If a multicenter trial, also discuss enrollment at other sites.**

Although significantly delayed due to COVID-19 and technical implementation hurdles, enrollment at both sites during 2021 & 2022 has been successful and on track with the projected study timeline.

Enrollment for this continuing review was defined as those who had completed only research procedures (i.e., research questionnaires) at both sites. We realized that in the prior continuing review, the number reported as enrolled was the number who completed both clinical and research procedures rather than research procedures only. This is why ERICA seems to have a negative number within the progress of the sites within this application. At the last CR the number enrolled should have been the 157 individuals completing research procedures. Between sites, we have enrolled 150 participants since the last CR, for a total enrolled of 307 between sites.

IRB_00115509 - CR_12/15/2022 9:44 AM

Created: 12/15/2022 9:44 AM

PI: [name]

Submitted: 1/19/2023

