From the beginning of the study, how many participants signed consent forms but did not end up participating in the study?

0

Enrollment since the last continuing review approval at this site:

71 Reported enrollment during the last continuing review

27 Number enrolled since the last continuing review

Problems and Events

Have any unanticipated problems or adverse events involving risks to participants occurred since the last IRB approval?

Yes No

Have there been any complaints about the research since the last IRB review?

Yes No

Local HRPP Reporting

Have any significant financial conflicts of interest for study personnel been identified since the last approval that have not been reported to the IRB?

Yes No

Have there been any changes to human research protection reviews or approvals from your institution since last approval that have not been reported to the IRB.

Yes No

Title: Broadening the Reach, Impact, and Delivery of Genetic Services

Study Location Questions

University of Utah**Site Status****What is the enrollment status for this site?**

Permanently closed to enrollment of new participants

Will consent forms be used to re-consent participants after this application is approved? Yes No**Select all of the remaining research activities that will be performed at this site after approval of this continuing review:**

Data and/or biospecimen analysis

Indicate the type(s) of data/biospecimens are being analyzed:

Identifiable private data/biospecimens

A HIPAA Limited Data set

1,920 consent cover letters sent; up to 20,000 EHR records

Number of currently approved enrollments for this study as a whole960**Number of currently approved enrollments for this study location****Enrollment since the beginning of the study at this site:**237**Total number enrolled as of today's date at this site****From the beginning of the study, how many non-English speakers have been enrolled?**

2

Which non-English languages were used in the enrollment process since the last review?Yes **Spanish**

How many Spanish fully translated long forms were 2 How many Spanish short forms were 0 used?

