**Mandarin**

Nepali**Vietnamese****Russian****Other**

From the beginning of the study, how many participants signed consent forms but did not end up participating in the study?

0

Enrollment since the last continuing review approval at this site:

236 **Reported enrollment during the last continuing review**

1 **Number enrolled since the last continuing review**

Problems and Events

Have any unanticipated problems or adverse events involving risks to participants occurred since the last IRB approval?

Yes No

Have there been any complaints about the research since the last IRB review?

Yes No

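### The Aim 3 Analysis compares arms on questionnaire outcomes among responders with no non-response adjustment, although completers were about 33% of invitees in January 2023 (about 52% at Utah, 15% at NYU)

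*Combined protocol and SAP*

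**What the plan says.** The Aim 3 Analysis (section 4, Study Information, item 9) opens with two-group tests: "We will test bivariate relationships between the outcome variables and study arm", using t or Wilcoxon tests for continuous outcomes and chi-square or Fisher tests for categorical ones. It then carries over the Aim 2 multilevel regression procedure, in which covariates enter if significant in unadjusted analyses. It says nothing about patients who do not return a questionnaire. The Aim 3 sample size is 1,100, with no response rate stated. The only attrition allowance, about 10%, belongs to Aim 2.

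The cognitive, affective and communication outcomes come from Questionnaires 1 and 2 (item 6, Research Procedures). Adherence is treated differently: it uses self-reported screening and also EHR data, and the EHR is to be tracked for patients whom the decision-support algorithms identify.

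The plan does look at non-participants. Research Procedures item 5 says questionnaire returners will be compared with similar cohorts outside the questionnaire study. The waiver requests keep non-identifying recruitment data to "compare differences between those who did and did not participate in the research questionnaires". The listed items include demographics, race/ethnicity, genetic counseling and testing, and portal reading and response history. Nothing says this comparison will feed into the arm contrasts.

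The continuing review created 12/15/2022 and submitted 1/19/2023 reports for Utah "To date, appox. 450 participants have been invited to participate in Questionnaire #1" and for NYU "To date, 480 participants have been invited to participate in Questionnaire #1". It counts completion of research procedures only, "for a total enrolled of 307 between sites".

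**The concern.** When about two thirds of invitees have not completed a questionnaire, the arm comparison is made in a self-selected group. If the kind of patient who responds differs between arms, a difference, or an apparent lack of one, can reflect who answered and not the delivery model. Equal overall response in the two arms does not protect against this.

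There is a plausible route. The invitation to the questionnaires goes out through the patient portal. The patient-directed arm receives its education and testing offer through the same portal, while the enhanced arm has in-person or telephone counseling. A likely predictor of response, portal activity, is therefore tied to how one arm is delivered. Response also differs about 3.5-fold between the two health systems, and health system is not named in the Aim 2 covariate list that Aim 3 inherits.

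**Working it through.** **1. The plan's own Aim 3 figure.** Inputs from Aim 3 Sample Size: N = 1,100, effect size 0.02 (read here as Cohen's f²), 2 tested variables, 20 covariates, alpha 0.05. Power comes from the noncentral F with df1 = 2, df2 = N − 23 and λ = 0.02·N. At N = 1,100 it is 0.991, so the stated power above 90% holds if 1,100 independent responses are obtained.

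**2. Response at January 2023.** Invitations are those quoted from that review. Completers by site are 236 and 71 in its site table. The following year's review repeats them: "236 Reported enrollment during the last continuing review" (Utah) and "71 Reported enrollment during the last continuing review" (NYU). They sum to the stated 307.
- Utah: 236/450 = 52.4%. If the approximate 450 means 425 to 475, the range is 55.5% to 49.7%.
- NYU: 71/480 = 14.8%.
- Overall: 307/(450 + 480) = 307/930 = 33.0%.
- Utah supplies 236/307 = 76.9% of completers but 450/930 = 48.4% of invitations.

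**3. January 2024.** Completers were 237 and 98, total 335. Invitations were not updated. On the 2023 denominators the rates are 237/450 = 52.7%, 98/480 = 20.4% and 335/930 = 36.0%, and lower if more patients were invited.

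**4. How a false difference could arise (hypothetical).** Assume no true arm effect, half of invitees active on the portal, and outcome rates of 60% in active and 40% in inactive patients.
- Enhanced arm, response 33% in both groups: responders show 0.5×0.60 + 0.5×0.40 = 50.0%.
- Patient-directed arm, response 50% and 16%: overall response is again (50 + 16)/2 = 33%, and responders show (0.50×0.60 + 0.16×0.40)/(0.50 + 0.16) = 0.364/0.66 = 55.2%.
- The crude difference is 5.2 points, about half the ±0.10 margin stated for Aim 2. Aim 3 states no margin.
- Within each portal group the arm difference is zero, so the artefact appears only in a crude comparison or in a model without portal activity.
- Weighting by inverse response restores the patient-directed arm: (0.25×2×0.60 + 0.08×6.25×0.40)/(0.25×2 + 0.08×6.25) = 0.50.

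**5. Price of weighting.** Kish effective n = (Σw)²/Σw², with the simplest weights, invited/completed by site.
- 2023: 930²/(450²/236 + 480²/71) = 864,900/4,103.1 = 211, or 69% of 307. Power from step 1 is 0.59 at 307 and 0.43 at 211.
- 2024 completers on the 2023 denominators: 864,900/(450²/237 + 480²/98) = 270. Power is 0.63 at 335 and 0.53 at 270.

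These powers ignore clustering, which would lower them. The effect of weighting on EHR covariates cannot be computed from the documents.

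**The case against.** Several points on the other side stand.

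- A reader might infer that Aim 3 rests entirely on returned questionnaires. It does not: adherence, the outcome in the Aim 3 hypothesis, also uses EHR data on patients who need not have returned anything.
- A reader might infer from the site gap that the arm contrast is biased. The documents give response by health system and never by arm, and a gap between systems does not by itself bias a comparison of arms. The response pattern in step 4 is invented to show the mechanism.
- The portal route is softened in practice. Portal access was required for the questionnaires in both arms, non-responders receive up to three phone calls, and telephone and mail completion are offered.
- The rates are interim. The Utah denominator is approximate, and the numerator counts completion of either questionnaire.
- Item 9 asks only for a summary of methods, and a fuller protocol is cited that is not available here. The silence may not be a deliberate choice of complete-case analysis.

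The strongest statistical objection is that the planned regressions already adjust for patient-level variables, and that regression conditioning on the predictors of response needs much the same assumption as weighting. This stands only in part. Portal activity and health system are not named as covariates. Testing status and portal reading arise after randomisation, so putting them in the outcome model could adjust away part of the arm effect. A response model can use them without that cost.

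One limit remains: only patients who received genetic services are invited, a group formed after randomisation. Weighting back to all invitees does not restore the randomised comparison.

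**Conclusion.** The concern holds for the questionnaire-based Aim 3 outcomes: cognitive, affective, communication and self-reported screening. The plan gives no adjustment or sensitivity analysis for non-response. At the January 2023 snapshot completers were about 52% of invitees at Utah, 15% at NYU and 33% overall, with NYU at most about 20% a year later if invitations did not fall below 480.

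Bias in the arm contrast is a risk whose size is unknown; the 5-point figure is an illustration under assumed rates. The planned comparison of participants with non-participants shows that the team foresaw the issue. What is missing is the link from that comparison to the arm contrasts.

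A reader might also take it that the data for correction are already in hand. The documents support only that they are to be collected and retained under the waivers. The conclusion assumes that the retained data can be linked to arm, health system and invitation status.

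**What to change.** In the Aim 3 Analysis:

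1. Report questionnaire response by arm and by health system, separately for Questionnaires 1 and 2.
2. Prespecify a sensitivity analysis of the questionnaire outcomes that weights responders by stabilised inverse probability of response, stabilised on arm and health system. Fit the response model on all invited patients, using arm, health system, testing status, demographics, race/ethnicity, and portal reading and response history. Keep health system in the weighted outcome model and use clinic-robust standard errors.
3. Show weighted and unweighted results side by side. If they disagree, by a rule written beforehand, do not claim a difference or equivalence for that outcome.

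Rurality is not on the waiver lists, so the response model above does not rely on it.

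The cost is extra analysis and lower precision. Site-only weighting would reduce 307 completers to an effective 211. Stabilising on health system avoids that between-site part of the loss, but variation of weights within site adds its own. Weighting corrects only for recorded predictors, and only among invitees. For these reasons it is proposed as a sensitivity analysis and not as the main one.

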PROTOCOL TITLE: Broadening the Reach, Impact, and Delivery of Genetic Services (BRIDGE)

NCT NUMBER: NCT03985852

PROTOCOL DATE: 06/05/2019

The full trial protocol is available at:

[name], [name], [name], et al. Comparing models of delivery for cancer genetic services among patients receiving primary care who meet criteria for genetic evaluation in two healthcare systems: BRIDGE randomized controlled trial. *BMC Health Sciences Research*. 2021;21:542. doi:10.1186/s12913-021-06489-y

Date: Tuesday, August 6, 2024 10:49:19 AM

[Print](#)[Close](#)**IRB_00123563****Created:** 6/5/2019 3:01 PM**PI:** [name]**Submitted:** 3/5/2019**Title:** Broadening the Reach, Impact, and Delivery of Genetic Services**IRB_00123563**

1. Contacts and Title

1. Study Introduction

1. Responsible Investigator:

[name]

Email	Training	Col Date
[contact]	4/25/2022 SMCG	3/19/2024

a. Position of the Investigator:

Faculty or Non-Academic Equivalent

Student

Staff

Resident/Fellow

Other

2. Contact Persons for the Responsible Investigator:

Name	Email	Training
[name]	[contact]	2/22/2023 MCG
[name]	[contact]	3/4/2024 SMCG
[name]	[contact]	3/21/2022 SMCG
[name]	[contact]	1/9/2023 SMCG

3. Guests of the Responsible Investigator:

Last Name	First Name	E-Mail
[name]	[contact]
[name]	[contact]
[name]	[contact]
[name]	[contact]
[name]	[contact]

4. What type of application is being submitted?

New Study Application (or Amendment/Continuing Review)

5. Title Of Study:

Broadening the Reach, Impact, and Delivery of Genetic Services

6. Study Purposes and Objectives:

The proposed study will employ an implementation science framework to compare two models of genetic services delivery for 1,920 patients in a randomized controlled trial with clinic-level randomization. We hypothesize that uptake of genetic testing (Study Aim 2) and adherence to management recommendations (Study Aim 3) will be equivalent between the genetic services delivery models. We propose the following Specific Aims:

Aim 1) Identify primary care patients who qualify for genetic risk assessment in two healthcare systems using a CDS infrastructure to automatically evaluate family history.

*This aim has already been studied in IRB #105797. We will be utilizing this tool that is now available. Aim 1 will not be analyzed in this protocol but is part of our overall research model.

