Sample size for Aim 2 was calculated using PASS 15 based on an equivalence test for the difference of two proportions in a cluster-randomized design. Sample sizes of 480 in the patient-directed arm and 480 in enhanced standard of care arm, which were obtained by sampling 32 clusters (clinics) with 15 participants each and 16 clusters (clinics) with 30 participants each, respectively, achieve 80% power to detect equivalence. The margin of equivalence, given in terms of the difference between proportions, extends from -0.10 to 0.10. The calculations assume Likelihood Score Tests (Farrington & Manning) were used with an ICC of 0.05, and a significance level of 0.05. We believe that this is likely an overestimate of ICC based on our prior work. This sample size is sufficient for a multilevel multivariable regression analysis and achieves >95% power to detect a small effect size (0.02) attributable to 1 independent variable using an F-Test with an alpha of 0.05, adjusted for an additional 20 independent variables. To examine effect modification, sample size is calculated based on logistic regression of a binary response variable (Y) on a binary independent variable (X) and a binary confounder variable (Z). A sample size of 1,710 observations achieves 80% power at a 0.05 significance level to detect the X-Z interaction odds ratio of 1.5, using a two-sided Wald test. We will therefore enroll 1,920 patients in the Aim 2 trial to allow for about 10% attrition.

Aim 3 Analysis

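### Aim 3 hypothesises equivalent adherence, but the plan tests and sizes Aim 3 only for a difference and states no margin, equivalence rule, expected rate or ICC for adherence

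*Combined protocol and SAP*

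**What the plan says.** The hypothesis (1. Study Introduction, item 6) is that uptake of testing (Aim 2) and "adherence to management recommendations (Study Aim 3) will be equivalent between the genetic services delivery models".

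For uptake, 4. Study Information, item 9 follows this through. The Aim 2 analysis announces a test for equivalence. The Aim 2 sample size is an equivalence calculation for a cluster-randomised comparison: "The margin of equivalence, given in terms of the difference between proportions, extends from -0.10 to 0.10", based on "32 clusters (clinics) with 15 participants each and 16 clusters (clinics) with 30 participants each", "with an ICC of 0.05, and a significance level of 0.05". It adds that 0.05 probably overstates the ICC.

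For adherence, the same item does not. The Aim 3 analysis says "We will test bivariate relationships between the outcome variables and study arm using Student's t-test", with Wilcoxon, chi-square or Fisher tests where needed, followed by multilevel regression and interaction tests. The Aim 3 sample size reads "We estimate a sample size of 1,100 for a multilevel multivariable regression analysis with >90% power to detect a small effect size (0.02"). That effect belongs to two variables, tested jointly by an F-test at the 0.05 level. The section continues: "The variables tested are adjusted for an additional 20 independent variables". A second figure, 1,710, is given for an interaction odds ratio of 1.5. Nothing in Aim 3 mentions equivalence, a margin, an expected adherence rate or an ICC.

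**The concern.** Equivalence has to be shown by ruling out differences as large as a stated margin. A test of no difference does the reverse: its null hypothesis is the claim the investigators want to support, and failing to reject it is not evidence for it. As written, Aim 3 has no route from its data to its own adherence hypothesis.

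Adherence is one of only two outcomes named in the study hypothesis. Without a prespecified margin, equivalence could end up being claimed from a p-value above 0.05, or from a margin chosen after the data are seen. The power figure beside the 1,100 could also be taken as supporting the equivalence claim, which it does not address.

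**Working it through.** **1. The plan's own figure.** Inputs (Aim 3 Sample Size): N = 1,100, effect size f² = 0.02, 2 tested variables, 20 covariates, F-test at 0.05.
- Error df = 1,100 − 2 − 20 − 1 = 1,077; noncentrality = 0.02 × 1,100 = 22.
- Power is 99.1%. Reading 0.02 as R² also gives about 99%.
- The smallest N for 90% without clustering is 636. Dividing 1,100 by a design effect of 1.7 (15 per clinic, ICC 0.05) gives 647 and 90.5%. That may be where 1,100 comes from, but the plan does not say so.

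The stated power is therefore true as a statement about detecting an effect.

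**2. What equivalence power would be.** The documents give no inputs for adherence, so these are assumptions: Aim 2's margin (±0.10) and clinics (32 and 16), 550 patients per arm, two one-sided 0.05 tests, true difference 0, the same adherence proportion p in both arms, normal approximation.
- Patients per clinic: 550/32 = 17.19 and 550/16 = 34.38.
- Design effect = 1 + (m − 1) × ICC. At ICC 0.05: 1 + 16.19 × 0.05 = 1.81 and 1 + 33.38 × 0.05 = 2.67.
- SE = √[p(1 − p)(1.81 + 2.67)/550].
- Power = 2Φ(0.10/SE − 1.645) − 1.

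At p = 0.5, SE = √(0.25 × 4.48/550) = 0.0451, and power = 2Φ(2.217 − 1.645) − 1 = 43%.

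| Adherence | SE, ICC 0.05 | Power, ICC 0.05 | Power, ICC 0.02 | Power, ICC 0 |
|---|---|---|---|---|
| 50% | 0.0451 | 43% | 71% | 90.5% |
| 30% or 70% | 0.0414 | 56% | 81% | 95% |
| 20% or 80% | 0.0361 | 74% | 92% | 99% |
| 16% or 84% | 0.0331 | 83% | 96% | >99% |
| 10% or 90% | 0.0271 | 96% | >99% | >99% |

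Farrington–Manning variances give nearly the same at ICC 0.05: 43.9%, 56.3% and 73.4% for the first three rows, and 94.7% for the last.

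**3. Check of the formula on Aim 2.** With 480 + 480 and design effects 1.70 and 2.45, the formula returns Aim 2's stated 80% if uptake is about 16% (or 84%). Aim 2 states no baseline proportion either.

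**4. The effect size in percentage points.** f² = 0.02 gives R² = 0.02/1.02 = 0.0196. If all of it lies on study arm, the difference is 2√[0.0196 × p(1 − p)]: 14.0 points at p = 0.5, 11.2 at 0.2, 10.0 at 0.15 and 8.4 at 0.1.

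**The case against.** The strongest reply is that item 9 asks only for a summary, that the title page says the full protocol is published elsewhere, and that Aim 3 is worded as a comparison covering many cognitive, affective and communication outcomes, for which sizing for a difference is legitimate. Much of this stands. It limits the point to what these documents state, and to adherence rather than all of Aim 3. It does not remove the mismatch: the hypothesis names adherence as equivalent, and the summary that sets a margin for uptake sets none for adherence.

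Four stronger readings are tempting, and the documents do not support them.
- **That the >90% is wrong, or is contradicted by the equivalence figures.** The plan claims it for detecting an effect, and for that it reproduces. The two powers answer different questions.
- **That 1,100 gives only 43–74% power.** That range needs adherence between 20% and 80%, which the documents do not give, and ICC 0.05, which the plan calls a likely overestimate and chose for uptake. Nor is 1,100 clearly the number for adherence, which also draws on EHR data. With 1,710 the same formula gives 55–83% at ICC 0.05.
- **That the likely result is an interval too wide to show equivalence.** At ICC 0.05, power is already above one half at 30% or 70% adherence. At ICC 0.02 it is at least 71% at every rate. A shortfall is a risk, not a forecast.
- **That the design effect size exceeds the 10-point margin.** This requires the whole effect to lie on arm, although two variables are tested, and adherence between 15% and 85%.

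**Conclusion.** The point holds as a mismatch between hypothesis and test. It is an error in the plan as written and rests on no numerical assumption: equivalence of adherence is hypothesised, only differences are tested and powered, and the documents give no margin or rule by which equivalence could be declared.

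The size of any power shortfall cannot be fixed from the documents. Under the borrowed margin and clinics, with 550 per arm and no true difference, equivalence power runs from about 43% to 96% at ICC 0.05 as adherence moves from 50% to 10% or 90%. It rises to at least 90% everywhere if there is no clustering. The breadth of that range follows from the missing rate and ICC.

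**What to change.** In the Aim 3 section of item 9, choose one of two routes.

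1. **Keep the equivalence hypothesis.** Prespecify an adherence margin on the risk-difference scale, with a justification; Aim 2's ±0.10 is available but needs its own argument for adherence. Declare equivalence only if the clinic-adjusted 90% interval for the difference lies wholly inside the margin. Say that the >90% refers to detecting a difference, and add the equivalence power for a stated adherence rate, ICC and N.
2. **Drop it.** Withdraw the equivalence wording for adherence in 1. Study Introduction, item 6, and report the estimated difference with its interval.

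Either route costs a few sentences and no patients; the first may also bring a less favourable power figure. The margin counts as prespecified only if it is fixed before adherence is compared by arm. The continuing review submitted in January 2024 reports analysis of primary outcomes under way, so the date on which the margin was set should be recorded.
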